6.9. Previous and Concomitant Therapy

Medication/Therapy will be classified into anatomical therapeutic chemical (ATC) drug classes using the latest version of the World Health Organization (WHO) drug dictionary.

6.9.1. Previous Therapy

Previous therapy is defined as the therapy that starts and ends prior to the date of first dose of study treatment in the Induction Dosing Period. If therapy start and/or end dates are missing or partial, the dates will be compared as far as possible with the date of first dose of study treatment in the Induction Dosing Period. If there is clear evidence to suggest that the therapy stopped

prior to the first dose of study treatment in the Induction Dosing Period, the therapy will be assumed to be previous only.

The following summaries will be provided for the ITT population:

- Previous therapy (captured in the *Prior Therapy: Psoriasis* eCRF page and *Concomitant Therapy* eCRF page) by WHO ATC Level 4 and WHO preferred term.
- Previous psoriasis therapy captured in the *Prior Therapy: Psoriasis* eCRF page to be summarized according to type (topical prescription therapy, topical non-prescription therapy, non-biologic systemic agent, biologic agent, non-biologic non-systemic agent, phototherapy) and therapy. The previous biologic agent will be further classified as tumor necrosis factor alpha (TNF- α) inhibitor (includes infliximab, etanercept, adalimumab, golimumab, certolizumab pegol), interleukin- (IL-) 12/23 inhibitor (includes ustekinumab), IL-17 inhibitor (includes secukinumab and brodalumab), and other (includes efalizumab, alefacept, or other biological agent).
- The number and percentage of patients with each reason for discontinuation of previous psoriasis therapy to be summarized by type and therapy.

6.9.2. Concomitant Therapy

Concomitant therapy for the Blinded Treatment Periods is defined as a therapy that starts before, on, or after the day of first injection in the Induction Dosing Period and before the last visit date in the Extension Period and continues into the Blinded Treatment Periods, that is, either no end date (the therapy is ongoing) or an end date on or after the day of first injection in the Induction Dosing Period. Note that concomitant therapy will belong to the Blinded Treatment Periods if it starts and ends on the exact same day as the day of first injection in the Induction Dosing Period.

Concomitant therapy for the Post-Treatment Follow-Up Period is defined as therapy that starts before, on, after the last visit date of the Extension Period and continues into the Post-Treatment Follow-Up Period, that is, either no end date (the therapy is ongoing) or an end date after the last visit date of the Post-Treatment Follow-Up Period.

The following summaries will be provided:

- Concomitant therapy by WHO ATC Level 4 and WHO preferred term for the ITT population during the Blinded Treatment Periods, and for the post-treatment follow-up population during the Post-Treatment Follow-Up Period, respectively.
- The number and percentage of patients taking concomitant therapy of topical product to be summarized for topical and topical steroid therapies, respectively, by WHO ATC Level 4 and WHO preferred term for the ITT population during the Blinded Treatment Periods. The definition of concomitant topical therapy can be found in the compound level safety standard.

Concomitant medications between treatment groups will be compared for the ITT population using Fisher's exact test.

If a partial or completely missing medication start date/time or end date/time is present, the following imputation rules will be utilized in the analysis:

- For the start date:
 - If year, month, and day are missing, then use the earlier of the patient’s first visit date or the consent date.
 - If either month or month and day are missing, then use 01 January.
 - If only day is missing, impute the first day of the month.
- For the start time:
 - Impute as 23:59
- For the end date:
 - If year, month, and day are missing, then use the patient’s last visit date.
 - If either month or month and day are missing, then use 31 December.
 - If only day is missing, then use the last day of the month.
 - The imputed date will not be beyond the patient’s last visit date.
- For the end time:
 - Impute as 23:59.
- If there is any doubt, the medication will be flagged as concomitant.

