### **5.1.4. Post-Treatment Follow-Up Period (Period 4)**

All patients receiving at least 1 dose of study drug will enter the Post-Treatment Follow-Up Period (Period 4) for a minimum of 12 weeks, beginning after their last regularly scheduled visit (or the date of their ETV).

Required study visits should occur at 4 weeks (Visit 801) and at 12 weeks (Visit 802) after the last regularly scheduled visit (or the date of the patient's ETV), except for patients with a concurrent infection that requires systemic anti-infective therapy (described in Section 9.4.6.1).

If, at Visit 802, a patient's neutrophil count is  $\geq 1500$  cells/ $\mu\text{L}$  or greater than or equal to the patient's baseline neutrophil count, the patient's participation in the study will be considered complete unless the investigator determines additional follow-up may be necessary. An additional study visit (Visit 803) 12 weeks after Visit 802 may be required. Additional visits before Visit 803 may be required for appropriate patient management (described in Section 9.4.6.1).

For patients who have entered Period 4, Ps therapy is allowed, as determined appropriate by the investigator. These allowed Ps therapies include the treatment patients received during the double-blind trial.

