#### 10.3.4.1. Adverse Events

Adverse events are classified based upon the Medical Dictionary for Regulatory Activities (MedDRA). A TEAE is defined as an event that first occurred or worsened in severity after

baseline and on or prior to the date of the last visit within the treatment period. Both the date/time of the event onset and the date/time of the first study drug injection are considered when determining TEAEs. Treatment-emergent adverse events will be assigned to the treatment period in which they first occurred or worsened. A follow-up emergent AE (FEAE) is defined as an event that first occurred or worsened in severity after the date of Week 24 or the ETV. For events that are gender specific, the denominator and computation of the percentage will include only patients from the given gender.

An overall summary of AEs will be provided for each of the treatment periods, including the number and percentage of patients who experienced TEAEs, TEAEs by maximum severity, deaths, SAEs, TEAEs related to study drug, discontinuations from the treatment due to an AE, and treatment-emergent AESIs. Treatment-emergent AEs (all, by maximum severity, and TEAEs possibly related to study drug by the investigator), SAEs including deaths, and AEs that lead to treatment discontinuation will be summarized and analyzed by MedDRA System Organ Class, and Preferred Term.

In addition to general safety parameters, safety information on specific topics of AESIs will also be presented. Potential AESIs will be identified by a standardized MedDRA query or a Lilly defined MedDRA preferred term listing.

Follow-up emergent adverse events, SAEs including deaths, and AEs that lead to study discontinuation will be summarized for Post-Treatment Follow-Up Period (Period 4).

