6.14.3. Deaths, Other Serious Adverse Events, and Other Notable Adverse Events

By-patient listings of deaths, SAEs, AEs leading to discontinuation will be provided, respectively.

All deaths will be included, regardless of the investigator's or the Sponsor's judgment about causality, including:

- any deaths occurring during participation in the study in the database for which data are being presented
- any deaths occurring after a patient leaves (is discontinued from or completed) the study in the database for which data are being presented if the death is:
 - the result of a process initiated during the study, regardless of when it actually occurred, or
 - occurs during the Period 4 after discontinuation of study drug.

The following summary tables (including treatment comparison) will be provided for the safety population for the Blinded Treatment Periods:

- SAEs by SOC and PT
- AEs that lead to treatment discontinuation (including death) by SOC and PT.

Follow-up emergent serious adverse event (FESAE) is defined as an SAE that first occurred or worsened in severity after the date of Visit 12 (that is, Week 24) or the ETV. The following summary tables will be provided for the follow-up population for the Post-Treatment Follow-Up Period:

- Follow-up emergent SAEs (FESAEs) by SOC and PT
- FEAEs that lead to treatment discontinuation (including death) by SOC and PT.

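### Two SAP rules for descriptive Period 4 displays use the wrong reference: the end-date test for follow-up concomitant therapy, and the type of discontinuation in the follow-up AE table

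*SAP*

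**What the plan says.** **Concomitant therapy.** SAP 6.9.2 describes a Period 4 therapy as one that "continues into the Post-Treatment Follow-Up Period, that is, either no end date (the therapy is ongoing") or has "an end date after the last visit date of the Post-Treatment Follow-Up Period". The paragraph just above it, for the Blinded Treatment Periods, asks instead for no end date or "an end date on or after the day of first injection in the Induction Dosing Period". For incomplete end dates the same section adds a cap: "The imputed date will not be beyond the patient’s last visit date". It closes with a rule that a medication is treated as concomitant when its timing is in doubt.

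**Follow-up AE table.** SAP 6.14.3 lists for Period 4 a table of "FEAEs that lead to treatment discontinuation (including death) by SOC and PT". Protocol 10.3.4.1 plans something different for the same period: "Follow-up emergent adverse events, SAEs including deaths, and AEs that lead to study discontinuation will be summarized".

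**Background.** SAP 6.14.2 defines an FEAE as an event that begins or worsens after Visit 12 (Week 24) or the ETV. Protocol 5.1.4 permits psoriasis therapy in Period 4 at the investigator's discretion, and adds: "These allowed Ps therapies include the treatment patients received during the double-blind trial". SAP 6.14 summarizes Period 4 safety by the treatment received in the Blinded Treatment Periods.

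**The concern.** Whether a therapy continues into a period depends on where its end date lies relative to the start of that period. The Period 4 rule compares it with the end. A therapy begun and finished inside follow-up, or carried in and stopped there, therefore fails the definition even though it was taken during follow-up.

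This table is the only Period 4 medication summary that SAP 6.9.2 lists; the topical-therapy summary covers the Blinded Treatment Periods only. Patients may take psoriasis therapy in Period 4 while their safety data are still shown under the treatment from the blinded periods. A reader would use this table to see what else they were taking, and short courses, such as an anti-infective for an infection in follow-up, would be missing.

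The AE table asks which follow-up events made patients stop a treatment that they had already stopped. The protocol's question, which events made patients leave the study, has no corresponding SOC/PT table in SAP 6.14.3.

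**Working it through.** The plan gives no figure on this point, so there is none to reproduce. The check applies the written rules to the visit schedule.

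**(a) Concomitant therapy**

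Inputs, from the protocol's Schedule of Activities: Week 24 is nominally day 168; Visit 802 is 12 weeks after the last treatment-period visit; Visit 803 is 24 weeks after it.

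- Visit 802: 168 + 84 = day 252
- Visit 803: 168 + 168 = day 336

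Take every possible known end date in Period 4, from day 169 to the last follow-up visit. The literal rule keeps it if the end day is later than the last Period 4 visit. The start-of-period rule keeps it if the end day is later than day 168.

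| Last follow-up visit | Possible end days | Kept, literal rule | Kept, start-of-period rule |
|---|---|---|---|
| Visit 802 (day 252) | 252 − 168 = 84 | 0 | 84 |
| Visit 803 (day 336) | 336 − 168 = 168 | 0 | 168 |

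An imputed end date is at most the patient's last visit date. Taking that as the last Period 4 visit, it can equal that date but not exceed it, so it fails the literal rule. If imputed to the last visit, it passes the start-of-period rule. The separate rule for doubtful timing may still bring in a partial or missing date; it does nothing for a known one.

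Under the literal rule the table therefore keeps therapies that are ongoing, therapies with an end date after the last follow-up visit, and possibly some with unclear dates.

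**(b) Follow-up AE table**

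Inputs: the last scheduled dose is at Week 20, day 140 ± 5 (Schedule of Activities); a late dose after Week 12 is to be given within 5 days of the scheduled day (protocol 7.3.1); the Week 24 visit is day 168 ± 5.

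- Latest dose at the edge of the visit window: 140 + 5 = day 145
- Latest dose if a 5-day delay is added to that: 145 + 5 = day 150
- Earliest Week 24 visit: 168 − 5 = day 163

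For a completer, the last dose precedes the earliest start of the FEAE window by at least 163 − 150 = 13 days, and no further dose is planned. A patient who stops drug early attends the ETV before entering Period 4 (protocol 5.1), so drug has stopped before the FEAE window opens. An event that caused the stop began before the ETV. SAP 6.14.2 also says that an event already counted as treatment-emergent is not counted again as an FEAE.

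A new non-fatal FEAE therefore cannot lead to discontinuation of study drug. A fatal FEAE can enter, because the table's title includes death.

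**The case against.** The strongest reply is that the intent of 6.9.2 is plain from its own sentence and a competent programmer would code it correctly. That is likely, but it would mean departing from the written definition, so the text still needs correcting.

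Several stronger readings are tempting, and the documents do not support them.

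- *A reader might infer that the AE table must be empty.* It need not be: the title includes death, so fatal FEAEs qualify. An event that caused drug withdrawal and then worsened after the ETV might also be argued in, since worsening is part of the FEAE definition. The rule against double counting appears to remove it.
- *A reader might infer that every therapy that ended is lost.* Therapies with an end date after the last follow-up visit stay, and the doubt rule may rescue some partial or missing dates. A therapy begun before the last Extension Period visit and stopped in Period 4 still appears in the Blinded Treatment Periods table. Among known end dates, it is mainly therapies both started and stopped within Period 4 that go missing from both tables.
- *A reader might infer that post-study psoriasis treatment would be hidden.* Maintenance therapy still in use at the last follow-up visit has no end date and is kept. Short or stopped courses are what drop out.
- *A reader might infer that Period 4 discontinuations go unreported.* SAP 6.5 lists and summarizes study disposition, with reasons, for the follow-up population. SAP 6.14.2 lists all AEs, and 6.14.3 lists AEs leading to discontinuation without limiting them to treatment. What is missing is the SOC/PT summary.

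It is also fair to say that protocol 10.3.2.3 asks for concomitant-medication summaries by treatment period, so a Period 4 table goes beyond that requirement. Once planned, it should still be defined correctly.

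**Conclusion.** Wrong as written, and minor. Read literally, the Period 4 concomitant-therapy rule excludes every therapy with a known end date on or before the last follow-up visit (0 of 84 or 0 of 168 end days kept), against its own stated intent and the parallel rule in the same section. The follow-up discontinuation table is in effect limited to fatal events, and the protocol's SOC/PT summary of AEs leading to study discontinuation is not specified.

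The day counts use nominal visit days and treat the patient's last visit as the last Period 4 visit. The documents do not say how many therapies will end within Period 4, so the number of patients affected is unknown.

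Both displays are descriptive. SAP Table RHCR.6.2 plans no treatment comparison in Period 4, and the Fisher's exact comparison of concomitant medications in 6.9.2 is for the ITT population. No primary, major secondary or between-group comparison changes.

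**What to change.** Two wording corrections in the SAP.

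- **6.9.2:** define Period 4 concomitant therapy as therapy with a start date on or before the last follow-up visit and either no end date or an end date after the last visit of the Blinded Treatment Periods (Week 24 or ETV). The ETV must be named, because patients who leave during the Induction Dosing Period have no Extension Period visit.
- **6.14.3:** retitle the follow-up table as FEAEs that lead to study discontinuation (including death), by SOC and PT, which brings it into line with protocol 10.3.4.1.

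The cost is two phrases in the SAP and the matching table specifications. Neither change calls for a new kind of analysis.

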6.10. Treatment Compliance

Throughout the Blinded Treatment Periods, trained unblinded site personnel will record information in a Study Drug Administration Log (captured in the *Exposure* eCRF page), including the date, time, and anatomical location of administration of study drug, syringe number, and the reason if the study drug was not fully administered.

Treatment compliance (%) for each patient will be calculated as:

$$100 \times \frac{\text{Total number of injections administered}}{\text{Total number of injections prescribed}}$$

- Number of injections prescribed (that is, expected) during the Blinded Treatment Periods is 10 for patients completing the Blinded Treatment Periods.
- For patients who discontinue during the Blinded Treatment Periods, the number of injections prescribed can be derived from the IWRS study drug dispense dataset.
- The total number of injections administered will be derived using the response to the question, “Was dose administered?” on the *Exposure* eCRF page.

A patient will be considered overall compliant with study treatment if he/she misses no more than 20% of the expected doses, does not miss 2 consecutive doses, and does not over-dose (that is, take more injections at the same time point than specified in the protocol).

Patient treatment compliance during the Blinded Treatment Periods will be summarized for the safety population. The comparisons between treatment groups will be conducted using Fisher’s exact test.

6.11. Efficacy Analyses

Table RHCR 6.4 includes the description and derivation of primary and major secondary efficacy outcomes. Table RHCR 6.5 provides the detailed analyses including analysis type, method and imputation, population, time point, and treatment group comparisons for primary and major secondary efficacy analyses.

Table RHCR 6.4. Description and Derivation of Efficacy Outcomes

Measure	Description	Variable	Derivation/Comment	Processing of Missing Components
PASI	
PASI combines assessments of the extent of body-surface involvement in 4 anatomical regions (head/neck, trunk, arms, and legs) and the severity of scaling (S), redness (R), and plaque induration/infiltration (thickness [T]) in each region, yielding an overall score of 0 for no psoriasis to 72 for the most severe disease (Fredriksson and Pettersson 1978). Severity is rated for each index (R, S, T) on a 0-4 scale (0 for no involvement up to 4 for severe involvement):
 
0 = none 1 = slight 2 = moderate 3 = severe 4 = very severe
 
The body is divided into 4 anatomical regions comprising the head (h), upper limb (u), trunk (t), and lower limb (l). In each of these areas, the fraction of total body surface area affected is graded on a 0-6 scale (0 for no involvement; up to 6 for 90% - 100% involvement):
 
0 = 0% (clear) 1 = >0% to <10% 2 = 10% to <30% 3 = 30% to <50% 4 = 50% to <70% 5 = 70% to <90%
	PASI score	
The composite PASI score is calculated by multiplying the sum of the individual-severity scores for each area by the weighted area-of-involvement score for that respective area, and then summing the four resulting quantities as follows: $PASI = 0.1(R_h + T_h + S_h)A_h + 0.2(R_u + T_u + S_u)A_u + 0.3(R_t + T_t + S_t)A_t + 0.4(R_l + T_l + S_l)A_l$ where: R_h, R_u, R_t, R_l = redness score of plaques on the head, upper limb, trunk, and lower limb, scored 0-4, respectively; T_h, T_u, T_t, T_l = thickness score of plaques on the head, upper limb, trunk, and lower limb, scored 0-4, respectively; S_h, S_u, S_t, S_l = scaliness score of plaques on the head, upper limb, trunk, and lower limb, scored 0-4, respectively; A_h, A_u, A_t, A_l = numerical value translation of % area of psoriatic involvement score for the head, upper limb, trunk, and lower limb, respectively. PASI scores are treated as a continuous score, with 0.1 increments within these values.
	If any individual score is missing, the PASI score will not be calculated, hence, missing.
		PASI change from baseline	Calculated as: observed PASI – baseline PASI.	Missing if baseline or observed value is missing
		PASI percent improvement from baseline	Calculated as: $Percent\ improvement\ from\ baseline = 100 \times \frac{Baseline\ PASI - Observed\ PASI}{Baseline\ PASI}$ If a patient has experienced an improvement,	Missing if baseline or observed value is missing

Measure	Description	Variable	Derivation/Comment	Processing of Missing Components
	
6 = 90% to 100%
 
The various body regions are weighted to reflect their respective proportion of body surface area.
		this measure will be positive. If a patient has experienced a worsening in the condition, this measure will be negative.	
		PASI 50	A clinically meaningful response; at least a 50% improvement in PASI score from baseline.	Missing if baseline or observed value is missing.
		PASI 75	A clinically meaningful response; at least a 75% improvement in PASI score from baseline.	Missing if baseline or observed value is missing.
		PASI 90	Higher level of clearance; at least a 90% improvement in PASI score from baseline.	Missing if baseline or observed value is missing.
		PASI 100 (Primary)	Complete resolution of plaque psoriasis; a 100% improvement in PASI score from baseline.	Missing if baseline or observed value is missing.
		PASI ≤1	A PASI ≤1.	Missing if PASI is missing.
		PASI ≤3	A PASI ≤3.	Missing if PASI is missing.
		PASI ≤5	A PASI ≤5.	Missing if PASI is missing.
		Time to first PASI 50; Time to first PASI 75; Time to first PASI 90; Time to first PASI 100	Calculated as: (Date of first PASI 50 response in defined treatment period – Date of first dose + 1) / 7. If the date of first dose is missing, the date of randomization is used. Similarly for PASI 75, PASI 90, and PASI 100.	
sPGA	sPGA is the physician’s global assessment of the patient’s psoriasis lesions at a given time point (EMA 2004 [WWW]). Plaques are assessed for induration, erythema, and scaling, and an overall rating of psoriasis severity is	sPGA score	Range from 0 to 5: clear (0), minimal (1), mild (2), moderate (3), severe (4), or very severe (5).	Single item, missing if missing.
		sPGA (0,1)	An sPGA assessed as either 0 or 1, which represents a clinically meaningful response of minimal plaque severity or complete	Missing if sPGA is missing.

Measure	Description	Variable	Derivation/Comment	Processing of Missing Components
	given using the anchors of clear (0), minimal (1), mild (2), moderate (3), severe (4), or very severe (5).		resolution of plaque psoriasis.	
		sPGA (0)	An sPGA assessed as 0, which represents a clinically important endpoint indicating complete resolution of plaque psoriasis.	Missing if sPGA is missing.
Percentage of BSA	The investigator will evaluate the percentage involvement of psoriasis on each patient’s BSA on a continuous scale from 0% (no involvement) to 100% (full involvement), in which 1% corresponds to the size of the patient’s hand (including the palm, fingers, and thumb) (NPF 2009).	BSA	Collected as a single scale as part of PASI eCRF page. Range from 0% to 100%.	Single item, missing if missing.
		BSA change from baseline	Calculated as: observed BSA – baseline BSA.	Missing if baseline or observed value is missing.
		BSA ≤1	A BSA ≤1, which represents treat to target concept by NPF.	Missing if BSA is missing.
Physician’s Global Assessment of Disease Activity VAS	Overall assessment of the severity of the patient’s current psoriatic arthritis activity using a 100-mm horizontal VAS. The investigator making the assessment must be a rheumatologist or medically qualified physician.	Physician’s global assessment VAS score	Range from 0 to 100 mm: 0 represents no disease activity, 100 represents extremely active disease activity.	Single item, missing if missing.
		Physician’s global assessment VAS change from baseline	Calculated as: observed physician’s global assessment VAS – baseline physician’s global assessment VAS.	Missing if baseline or observed value is missing.
		Physician’s global assessment VAS percent improvement from baseline	Calculated as: $Percent\ improvement\ from\ baseline = 100 \times \frac{Baseline - Observed}{Baseline}$ If a patient has experienced an improvement, this measure will be positive. If a patient has experienced a worsening in the condition, this measure will be negative.	
PGA-F	Assessment of the severity of fingernail abnormalities in patients with nail psoriasis. The scale assesses the nail bed and nail matrix signs of disease on a 0 to 4 scale: clear (0), minimal (1), mild (2), moderate (3), or severe (4) (Hudgens et al. 2016)	PGA-F	PGA-F score is the maximum of observed nail bed and nail matrix scores. Range from 0 to 4: clear (0), minimal (1), mild (2), moderate (3), or severe (4).	If any nail bed or nail matrix score is missing, the PGA-F score will not be derived, hence, missing.

Measure	Description	Variable	Derivation/Comment	Processing of Missing Components
		PGA-F (0, 1)	A PGA-F assessed as either 0 or 1, which represents a clinically meaningful response of clear or minimal nail psoriasis.	Missing if PGA-F is missing.
		PGA-F (0)	A PGA-F assessed as 0, which represents a clinically meaningful response of clear nail psoriasis.	Missing if PGA-F is missing.

Abbreviations: BSA = body surface area; eCRF = electronic case report form; EMA = European Medicines Agency; NPF = National Psoriasis Foundation; PASI = Psoriasis Area and Severity Index; PGA-F = Physician's Global Assessment of Fingernail Psoriasis; sPGA = Static Physician Global Assessment; VAS = visual analog scale.

Table RHCR 6.5. Description of Efficacy Outcomes Analyses

Measure	Variable	Analysis Method (Sections 6.1.3 and 6.3)	Analysis Population (Section 6.1.1)	Comparison/Time Point	Analysis Type
PASI	PASI 50	CMH test with NRI; Fisher’s Exact test with NRI	ITT Population; ITT population with PASI ≥ 12	IXE vs. GUS at Week 1 and all other postbaseline visits	Major secondary analysis is CMH test with NRI for ITT population comparing IXE vs. GUS at Week 1 (Section 6.11.2). Other analyses and comparisons are exploratory (Section 6.11.3).
	PASI 75	CMH test with NRI; Fisher’s Exact test with NRI	ITT Population; ITT population with PASI ≥ 12	IXE vs. GUS at Week 2 and all other postbaseline visits	Major secondary analysis CMH test with NRI for ITT population comparing IXE vs. GUS at Week 2 (Section 6.11.2). Other analyses and comparisons are exploratory (Section 6.11.3).
	PASI 90	CMH test with NRI; Fisher’s Exact test with NRI	ITT Population; ITT population with PASI ≥ 12	IXE vs. GUS at Weeks 4 and 8, and all other postbaseline visits	Major secondary analysis CMH test with NRI for ITT population comparing IXE vs. GUS at Weeks 4 and 8 (Section 6.11.2). Other analyses and comparisons are exploratory (Section 6.11.3).
	PASI 100	CMH test with NRI; Fisher’s Exact test with NRI	ITT Population; ITT population with PASI ≥ 12	IXE vs. GUS at Week 12, Weeks 4, 8, 24, and all other postbaseline visits	Primary analysis is CMH test with NRI for ITT population comparing IXE vs. GUS at Week 12 (Section 6.11.1). Major secondary analysis CMH test with NRI for ITT population comparing IXE vs. GUS at Weeks 4, 8, and 24 (Section 6.11.2). Other analyses and comparisons are exploratory (Section 6.11.3).

Measure	Variable	Analysis Method (Sections 6.1.3 and 6.3)	Analysis Population (Section 6.1.1)	Comparison/Time Point	Analysis Type
	PASI score; PASI change from baseline; PASI percent improvement from baseline	MMRM; ANCOVA with mBOCF for the Blinded Treatment Periods	ITT Population	IXE vs. GUS at all postbaseline visits	Exploratory analysis (Section 6.11.3).
	PASI \leq 1	CMH test with NRI; Fisher’s Exact test with NRI	ITT Population	IXE vs. GUS at all postbaseline visits	Exploratory analysis (Section 6.11.3).
	PASI \leq 3	CMH test with NRI; Fisher’s Exact test with NRI	ITT Population	IXE vs. GUS at all postbaseline visits	Exploratory analysis (Section 6.11.3).
	PASI \leq 5	CMH test with NRI; Fisher’s Exact test with NRI	ITT Population	IXE vs. GUS at all postbaseline visits	Exploratory analysis (Section 6.11.3).
	Time to first PASI 50; Time to first PASI 75; Time to first PASI 90; Time to first PASI 100	Log-rank test Kaplan-Meier product limit method; Kaplan-Meier plot (survival curve)	ITT Population	IXE vs. GUS during the Blinded Treatment Periods	Exploratory analysis (Section 6.11.3).
sPGA	sPGA (0, 1)	CMH test with NRI; Fisher’s Exact test with NRI	ITT Population; ITT population with sPGA \geq 3	IXE vs. GUS at all postbaseline visits	Exploratory analysis (Section 6.11.3).
	sPGA (0)	CMH test with NRI; Fisher’s Exact test with NRI	ITT Population; ITT population with sPGA \geq 3	IXE vs. GUS at Week 12 and all other postbaseline visits	Major secondary analysis CMH test with NRI for ITT population comparing IXE vs. GUS at Week 12 (Section 6.11.2). Other analyses and comparisons are exploratory (Section 6.11.3).

Measure	Variable	Analysis Method (Sections 6.1.3 and 6.3)	Analysis Population (Section 6.1.1)	Comparison/Time Point	Analysis Type
BSA	BSA change from baseline	MMRM; ANCOVA with mBOCF for the Blinded Treatment Periods	ITT Population	IXE vs. GUS at all postbaseline visits	Exploratory analysis (Section 6.11.3).
	BSA _{≤1}	CMH test with NRI; Fisher’s Exact test with NRI	ITT Population	IXE vs. GUS at all postbaseline visits	Exploratory analysis (Section 6.11.3).
Physician’s Global Assessment of Disease Activity VAS	Physician’s global assessment VAS score; Physician’s global assessment VAS change from baseline; percent improvement	ANCOVA with mBOCF; MMRM for the Blinded Treatment Periods	ITT Population – patients with baseline psoriatic arthritis	IXE vs. GUS at all postbaseline visits	Exploratory analysis (Section 6.11.3).
PGA-F	PGA-F (0, 1) with at least a 2-point improvement from baseline; PGA-F (0) with at least a 2-point improvement from baseline	CMH test with NRI; Fisher’s Exact test with NRI	ITT Population – Patients with baseline PGA-F ≥3	IXE vs. GUS at all postbaseline visits	Exploratory analysis (Section 6.11.3).

Abbreviations: ANCOVA = Analysis of Covariance; BSA = Percentage of Body Surface Area; CMH = Cochran-Mantel-Haenszel; GUS = guselkumab 100 mg; ITT = Intent-to-Treat; IXE = ixekizumab 80 mg; mBOCF = modified baseline observation carried forward; MMRM = Mixed-effects Model of Repeated Measures; NRI = Nonresponder Imputation; PASI = Psoriasis Area and Severity Index; PASI 50/75/90/100 = at least a 50%/75%/90%/100% improvement from baseline in PASI score; PGA-F = Physician’s Global Assessment of Fingernail Psoriasis; sPGA=static Physician Global Assessment; VAS = Visual Analogue Scale; vs. = versus.

